- All those measures contribute to the installation of a ritual much appreciated by patients with ASD.
- Sponsor highly recommends that the same person in charge of study evaluations follows a given child during the study in order to minimize any potential bias in study assessments and to reduce the burden linked to the potential stress suffered by the child.
- Paediatric liquid formulation has been specially developed for this paediatric clinical program. This formulation showed a good acceptability and palatability profile in the phase II.

For the benefit of the study, bumetanide could be the first pharmacological candidate allowing the treatment of ASD core symptoms in paediatric population, acting on a key component of the disease pathophysiology (alteration of GABAergic neurons and circuits, the conversion of GABA-mediated neuronal excitation into inhibition during maturation of specific neuronal populations being reported to be altered in neurodevelopmental diseases such as autism).

Acting centrally as a NKCC1 inhibitor, bumetanide provokes reduction of intracellular chloride, switching the aberrant excitatory action of GABA into an inhibitory action, and therefore may restore important developmental capacities.

Consequently, as there is no drug treatment for core symptoms of ASD, we set up a study with bumetanide in young developing patients with ASD in order to reduce the ASD core symptoms and functional impairment and to improve quality of life. Studies are needed in paediatric population, childhood being a time when brain plasticity is at the greatest and where behavioural and educative interventions could have the most benefit.

For the risk for the patient, the safety profile of bumetanide is similar to that reported for other loop diuretics. The target organ is the kidney and the safety profile is related to the potent diuretic activity of the compound. Based on the safety experience gained at this stage of drug development in ASD (5 clinical studies described above), the safety profile of bumetanide in ASD children and adolescents seems comparable to the one observed in adult patients treated for oedema. Despite the penetration of bumetanide into brain, no toxic effects on the Central Nervous System have been observed.

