4.3. Measures to minimise bias

The following measures have been taken to avoid biases:

- This is a randomised, placebo-controlled study carried out in double-blind conditions. Active treatment (bumetanide) and placebo oral formulations will have the same appearance and the same taste.
- An Interactive Response System (IRS) will be used for the treatment allocation: bumetanide or placebo will be assigned at inclusion (W000) by balanced (ratio 1:1) randomisation, with stratification on the country and on the patient sex. The structure responsible for designing and constructing the randomisation list in blind will be the Center of Excellence Methodology and Valorisation of Data of I.R.I.S.
- Investigators in charge of diagnosis should have a deep knowledge on the Autism Diagnostic Observation Schedule, second edition (ADOS-2) and Autism Diagnostic Interview - Revised (ADI-R) diagnostic tools.
- Training sessions on assessment scales will be organized for the investigators prior to their involvement and their participation will be mandatory.
- In order to maintain the double-blind conditions, the main efficacy criterion (CARS2) will be assessed by an independent rater. This rater will not be involved with any aspect of medical management of the patient and will not have access to patient data. The independent rater will be instructed not to discuss what adverse event (if any) the patient is experiencing from his/her medication. Prior to being examined by the independent rater, patients and parent/legal representative(s) or caregiver (when applicable) will be instructed not to discuss what (if any) adverse event patient may be experiencing. As far as possible same independent rater will assess CARS2 for a given patient all along the study (from W000 till W052 and at least till W026) and, when possible, all the patients for a given site.
- The laboratory parameters will be performed by a central laboratory in order to centralize and harmonise the data, with the exception of Na^+/K^+ which should be monitored always locally when the patient is under treatment to quickly manage Potassium Supplementation when needed.
- In addition to immediate local safety reading for safety reasons, a centralized assessment will be performed for each ECG (central reading reports for ECG overrule local reading for inclusion/exclusion/withdrawal criteria).

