1.2.2. Type of randomisation

The treatment randomisation and allocation are centralised using an Interactive Response System (IRS) procedure. The treatment (bumetanide or placebo) is assigned at inclusion visit by a balanced, non-adaptive randomisation with stratification on country and gender.

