1.3. Determination of sample size

The sample size was estimated to meet the primary endpoint defined as the change in CARS2 from baseline to 6 months using a two-sided Student's test.

With a total of 170 patients, statistical significance should be established with a power of 90% and a type-one error of 0.05 for an effect size of 0.5 between groups.

Assuming around 15% prematurely withdrawal rate, the total number of patients to be included is 200.

Missing data will be imputed using a reference based multiple imputation with a jump-to-reference approach or a standard multiple imputation depending on the reasons of withdrawal. Simulations were carried out to evaluate the impact of this procedure on power under various scenarios. The results on 1000 simulations have shown that power does not drop under 80% in the worst-case scenario.

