Primary analysis: bumetanide will be compared to placebo on the primary efficacy endpoint in the RS, using a General Linear Model (see Appendix 5.1.1.1) including the fixed, categorical effect of treatment, gender and country as well as the continuous fixed covariate of baseline value.

GENERAL LINEAR MODEL (ANCOVA): change = baseline country gender treatment [1]

The assumptions underlying the model, as for instance, the normality and homoscedasticity of residuals and detection of outliers, will be checked.

Missing data handling:

- For all study premature withdrawals due to other reasons as well as for study premature withdrawals due to lack of efficacy or AE in placebo arm, missing data will be imputed in both arms using a multiple imputation based on similar patients in the same treatment arm (missing at random assumption).
- For study premature withdrawals due to lack of efficacy or AE in S95008 arm, missing data will be imputed using a reference based multiple imputation with a jump-to-reference approach (*missing not at random assumption*).
Missing data as well as data considered as missing for the primary analysis due to the strategy used to handle intercurrent event will be imputed in the same way.

Multiple imputation inference involves 3 consecutive phases.

1/ Imputation step:

A total of 100 imputed complete data sets will be generated.

The imputation step of missing data with a monotone pattern will be separated in several sequences:

- For all patients with study or drug premature withdrawals due to other reasons as well as for patients with study or drug premature withdrawals due to lack of efficacy or AE in placebo arm, the regression method (adjusted on the same covariates as the model [1] and considering all longitudinal data of planned visits) will be used to impute missing data (*i.e.* based on patient completers under corresponding treatment arm).
- For patients with study or drug premature withdrawals due to lack of efficacy or AE in S95008 arm, the imputation step will be done sequentially for each time point t separately (W4, W12 and W26) based on placebo patients with non missing data at the timepoint t . The regression method will be adjusted on the same covariates as model [1] except the treatment variable (which is a modified variable in order to consider the placebo data as reference for imputation) and considering all longitudinal data of planned visits up to timepoint t .

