A regression method will be used to perform the imputation, using in this order: baseline, baseline covariates (e.g. country, gender), treatment and variable of interest at the planned visits in the model. Of note, for imputing data of visit *i*, data up to visit *i-1* are to be considered for the imputation, even if the data of visit *i-1* already results of an imputation (this is taken into account in PROC MI with the order of the variables put in the VAR statement). This is applicable for variable of interest at each planned post-baseline visits.

Of note, for subgroup analysis, the subgroup should not be added as a covariate in the regression model.

b) For patients with study or drug premature withdrawals due to lack of efficacy or AE in S95008 arm

To impute those missing data, an input dataset will be prepared with data from all placebo patients (completers or with missing values regardless of the reason), and from S95008 patients, with missing data due to AE/lack of efficacy.

The jump-to-placebo approach will be set up for these patients' imputations, by using the %mistep macro from James Roger (<https://www.lshtm.ac.uk/research/centres-projects-groups/missing-data#dia-missing-data> , zip file MISTEP20180327).

A sequence of %mistep will be run, considering as the first model (for the first post-baseline visit): baseline baseline covariates (e.g. country, gender), treatment*. The subsequent model (for the second post-baseline visit) will include, in addition to variables included in the first model, the residuals of this first model (put at the end of the statement). The other subsequent models will be implemented in the same way.

**at each visit the treatment variable is derived such as the missing value in the S95008 will be imputed using the placebo arm as reference.*

This macro will be used because no SAS procedure are currently available to perform the jump to reference approach.

Step 3:

Finally we can assemble back all subjects with complete data: all patients from Step2a and remaining S95008 patients from Step2b (*DATA_COMPLETE*).

In case of imputed data at W026 (respectively W012 depending on the analysis) are outside of the endpoint ranges, the imputed data will be replaced by the boundary that was overpassed.

| Endpoint | Min | Max |
|--|-----|------|
| CARS2 total score | 15 | 60 |
| SRS2 total score | 0 | 195 |
| CGI-I | 1 | 7 |
| VABS II Adaptative Behavior Composite standard score | 20 | 160 |

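### No planned efficacy analysis uses age, although the trial enrols children from 2 to under 7; prespecifying it as a covariate is a small, cheap and conditional gain in precision.

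*SAP*

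**What the plan says.** **Randomisation.** Protocol 4.3 assigns treatment "by balanced (ratio 1:1) randomisation, with stratification on the country and on the patient sex". SAP 1.2.2 repeats this: "non-adaptive randomisation with stratification on country and gender".

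**Primary model.** SAP 3.4.2.1 fits "GENERAL LINEAR MODEL (ANCOVA): change = baseline country gender treatment [1". This follows Protocol 10.2.2.4.2, which names baseline CARS and the stratification factors as covariates. Protocol 10.2.2.4.3 does the same for SRS.

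**Imputation.** SAP 3.4.2.1 ties both regression steps to the covariates of model [1] plus the CARS2 values at planned visits. SAP 5.1.2, Step 2a, words the list as "baseline, baseline covariates (e.g. country, gender), treatment and variable of interest at the planned visits in the model". The preliminary MCMC step for intermittent gaps uses treatment group, baseline and the visit values.

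**Other analyses.** The MMRM (SAP 3.4.2.3 and 5.1.3) and the secondary models (SAP 3.4.3) have no age term. The only sensitivity analysis in SAP 3.4.2.2 drops country and gender. SAP 3.4.4 has no subgroup analysis.

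**Age in the design.** Protocol 5.1.1 admits children from 2 to under 7 years. Under Protocol 7.2, CARS2 is rated against a typically developing individual of the same age. The high-functioning form is available only from age 6, and then only with sufficient IQ and verbal skill. The SRS-2 form also depends on age.

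**The concern.** Five years is a wide span at this stage of development, and age at inclusion is known for every child. If six-month CARS2 change differs by age beyond what baseline score, country and sex explain, two things follow.

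- **Precision.** Age-related variation stays in the residual, so the standard error is larger than it needs to be. A chance difference in mean age between the arms is not adjusted for.
- **Imputation.** The missing-at-random step borrows from similar children in the same arm, and similarity is defined without age. If age predicts both withdrawal and outcome beyond the variables used, the assumption is weaker than it could be. The planned withdrawal of about 15% of 200 is 30 children.

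No listed analysis would show whether the result depends on age adjustment.

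**Working it through.** **1. Inputs from the documents (SAP 1.3).** The calculation rests on a two-sided Student's test of CARS2 change, with alpha 0.05, 90% power, a standardised effect of 0.5 and 170 evaluable children. On withdrawal the SAP states: "Assuming around 15% prematurely withdrawal rate, the total number of patients to be included is 200".

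**2. The plan's own figure.** The number per arm is 2 × (1.960 + 1.282)² / 0.5² = 84.1, rounded up to 85, or 170 in total. Exact (noncentral t) power at 85 per arm is 90.0%. Inflation for withdrawal gives 170 / (1 − 0.15) = 200. Both stated numbers reproduce, and neither takes credit for a covariate.

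**3. Assumptions, none of them in the documents.**
- The partial correlation r of age with CARS2 change, given baseline, country and sex, is 0 to 0.3.
- Ages are uniform over 2 to 7 years, so the SD is 5/√12 = 1.44 years.
- The planning SD is taken as the residual SD under model [1] without age.

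**4. Gain from adding age, at 85 per arm.** The SE is multiplied by √(1 − r²). The equivalent gain in patients is 1/(1 − r²) − 1. Power uses an effect of 0.5/√(1 − r²) with one degree of freedom fewer.

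| r | r² | SE lower by | Equivalent extra patients | Power |
|---|---|---|---|---|
| 0 | 0 | 0% | 0% | 90.0% |
| 0.1 | 0.01 | 0.5% | 1% | 90.3% |
| 0.2 | 0.04 | 2.0% | 4% | 91.1% |
| 0.3 | 0.09 | 4.6% | 10% | 92.5% |

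**5. Chance imbalance.** The SE of the difference in mean age is 1.44 × √(2/85) = 0.22 years, so the 95% limit is 1.96 × 0.22 = 0.43 years, or 0.30 age SDs. At that limit the treatment estimate shifts by r × 0.30 SD:
- r = 0.1: 0.03 SD, 6% of the planned 0.5 SD effect
- r = 0.2: 0.06 SD, 12%
- r = 0.3: 0.09 SD, 18%

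These are values at the 95% limit and random in direction. They are already part of the variance in step 4 and must not be added to it.

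**6. Validity check.** Simulation used 20,000 trials per setting, 85 per arm and a linear age effect.

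| r² | Type I error without / with age | Power without / with age |
|---|---|---|
| 0.05 | 5.0% / 4.9% | 90.0% / 91.3% |
| 0.10 | 4.9% / 5.0% | 89.6% / 92.2% |

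Leaving age out does not disturb the error rate, and power stays at about the planned level.

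**The case against.** The strongest reply is that model [1] already holds baseline and every stratification factor, as the protocol prescribes, and that one more covariate of unknown value is a matter of taste. Much of this stands.

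- **Is age prognostic?** A reader might infer that age drives the course of the disorder. The documents do not say so. Protocol 2 says that comorbidities and associated symptoms vary with age. Its remark on "childhood being a time when brain plasticity is at the greatest and where behavioural and educative interventions could have the most benefit" explains why paediatric studies are needed; it describes no gradient between 2 and under 7 and does not mention CARS2 change.
- **Absorption.** CARS2 is rated against same-age peers and baseline CARS2 is in the model, so some of any age effect may already be removed. The true r may be zero.
- **Imputation.** A reader might infer that a 2-year-old and a 6-year-old with the same baseline score are imputed identically. They are not. The regressions also use country, sex, treatment and any observed W004 and W012 scores, and the imputed values are random draws.
- **Other uses of age.** It would be too strong to say that the plan ignores age. Demographic data are described by arm to assess comparability (SAP 3.2 and 3.2.3), and withdrawn and completing patients are compared at inclusion (SAP 3.2.1). These tables can reveal an age imbalance or age-related withdrawal, but they adjust no efficacy estimate.
- **Cost.** The change is more than SAP wording, because the protocol itself fixes the covariate list.

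What remains is that age is collected, is a plausible prognostic factor and enters no efficacy analysis. The wording with e.g. in SAP 5.1.2 also leaves the imputation covariates open.

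**Conclusion.** The point holds as a minor, conditional improvement. No planned efficacy analysis uses age. Over an assumed partial correlation of 0 to 0.3, adding it would lower the SE by 0 to about 4.6% and raise power from 90.0% to at most about 92.5% at 170 evaluable children. If age adds nothing, the gain is nil.

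The omission might be read as biasing the primary estimate or leaving the trial underpowered. The documents support neither reading. Randomisation keeps the estimate unbiased, the type I error is 5% with or without age, chance imbalance is already reflected in the SE, and the stated 90% power does not rely on covariates.

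The imputation benefit depends on age predicting withdrawal as well as outcome beyond the variables already used. The documents give no figure from which to size it.

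**What to change.** Before unblinding:

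1. Add age at inclusion, as a continuous covariate, to model [1].
2. Add it to the imputation in SAP 5.1.2 (Steps 1, 2a and 2b), and replace the open-ended example there with a closed covariate list.
3. Add age and age-by-visit to the MMRM.
4. Make the same changes for SRS-2.
5. Keep the current model without age as a sensitivity analysis.
6. Record the change in the SAP version log as a departure from the covariate list in Protocol 10.2.2.4.2 and 10.2.2.4.3.

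If the sponsor prefers to leave model [1] as the primary analysis, the minimum is age in the imputation model plus a prespecified age-adjusted sensitivity analysis, or a written reason for leaving age out.

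The cost is one degree of freedom in the ANCOVA, a few in the MMRM, and a documented change to the SAP and protocol. No new data are needed. Stratification need not change, since covariate adjustment serves the purpose.

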3.4.2.2. Sensitivity analyses

- Unadjusted analysis:

The same primary analysis will be performed for the primary endpoint using a General Linear Model (ANCOVA) without any covariates. The following model will be considered instead of model [1]:

GENERAL LINEAR MODEL (ANCOVA): change = baseline treatment [2]

3.4.2.3. Supplementary analyses

- Treatment policy estimand:

The primary analysis will be repeated for the primary endpoint using all CARS2 values reported regardless of occurrence of treatment discontinuation.

In case of CARS2 values are still missing, the same imputation process as in the primary analysis will be performed for these individuals.

- Hypothetical estimand based on Mixed-effects Model for Repeated Measures

A Mixed-effects Model for Repeated Measures (MMRM) (see Appendix 5.1.3) using the longitudinal data at each planned post-baseline visit of the double-blind period (W004, W012 and W026) will be performed as if patients had continued their randomised treatment. In this analysis, all data occurring after all intercurrent events will be considered as missing. The comparison associated with the analysis will be the contrasts between Bumetanide and placebo for the change from baseline to W026 of the CARS2 total score. The model will include the fixed, categorical effects of country, gender, treatment, visit, treatment by visit interaction, country by visit interaction and gender by visit interaction as well as the continuous, fixed covariates of baseline and visit-by-baseline interaction:

*MMRM: change at each visit = baseline country gender treatment visit treatment*visit baseline*visit country*visit gender*visit [4]*

Statistical elements: the following elements will be provided in a summary table:

- Estimate (standard error) of the difference between adjusted treatment arm means.
- Two-sided 95% CI of the estimate.

- W012 analysis:

The primary analysis will be repeated for the CARS2 total score expressed in term of change from baseline to W012.

- CARS2 responders analysis:

Definition:

CARS2 responders will be defined as patients having an improvement of at least 4.5 points in the CARS2 total raw score as compared to baseline (Jurek *et al.*, 2021).

Main Analysis:

CARS2 responders at W012 and at W026 will be analysed using a logistic regression model with the fixed categorical effect of treatment, country and gender.

Note: In case of a complete separation of data (zero cell count in a treatment group), only descriptive statistics will be provided. In case of quasi-completed separation of data, a logistic regression with penalized maximum likelihood will be used (see Appendix 5.1.4).

Missing data handling:

The 100 datasets imputed for the primary analysis and supplementary analysis at W012 (based on the changes from baseline in CARS2 total scores) will be used to derive, the CARS2 responders. Analysis step will be based on the logistic regression model described above and then the combination step will be applied.

Statistical elements: the following elements will be provided in a summary table:

- Estimate (standard error) of the odds ratio between treatment groups.
- Two-sided 95% CI of the estimate.

- Descriptive analysis:

The CARS2 total score and subscores will be summarized using descriptive statistics and graphs (expect for subscores):

- During the double-blind period: baseline, each planned post-baseline visit (W004, W012 and W026) as well as change from baseline to each planned post-baseline visit will be described in the RS by treatment groups (S95008 vs placebo).
- During the open-label period: OL baseline, each OL planned post-baseline visit (W038 and W052) as well as change from OL baseline to each OL planned post-baseline visit will be described in the RSO for the Placebo/S95008 arm.
- During the combined period: baseline, each planned post-baseline visit as well as change from baseline to each planned post-baseline visit will be described in the RSC for the S95008/S95008 arm.
- At the follow-up visit (WEND), the change from the last post-baseline visit under treatment during the open-label period to WEND will be described in the RSO by treatment groups (S95008/S95008 vs Placebo/S95008).

The proportions of CARS2 responders will also be summarized at each planned post-baseline visit for each period.

The proportions of CARS2 performed remotely at baseline, W012 and W026 will be described in the RS by treatment groups (S95008 vs placebo).

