3.4.2. Primary efficacy endpoint

3.4.2.1. Primary analysis

Definition:

The primary estimand is defined according to the primary objective of the trial, which is to evaluate treatment effect:

- Taking into account the unfavorable outcome when patients are unable to continue taking the study drug due to an adverse event or for lack of efficacy.
- Independently of treatment discontinuations for non-medical reasons because those patients would have theoretically continued to be treated as planned in clinical practice.

The attributes of the primary estimand will be defined as following:

- Population: children and adolescents aged from 2 to less than 7 years old with Autism Spectrum Disorder.
- Variable: change in CARS2 total score from baseline to W026.
- Summary measure: difference in means.
- Intercurrent events:
 - Treatment discontinuation due to lack of efficacy or AE (*hypothetical strategy*):
 - For S95008 arm, the quantification of the treatment effect cannot ignore the situation where a patient can no longer tolerate or benefits from the treatment, from whom a continuation of the treatment would not be conceivable. Bumetanide is a treatment with a rapid onset and short duration of action. So, the assumption that the treatment benefit in patients who discontinue the active arm disappears immediately upon discontinuation is clinically meaningful. CARS2 values after this intercurrent event will be considered as missing and imputed using a reference based multiple imputation (“jump-to-reference” approach).
 - For placebo arm, it will be considered as if patients were stayed under placebo, and CARS2 values after the intercurrent event will be considered as missing and imputed using a multiple imputation (MAR approach).
 - Treatment discontinuation for other reason (*hypothetical strategy*): a reasonable question is what difference is attributable to treatment if no such events occurred namely if patients were stayed under their randomised treatment. CARS2 values after the intercurrent events will be considered as missing and imputed in both arms using multiple imputations (MAR approach).

Primary endpoint: the primary efficacy endpoint is defined as the change from baseline to W026 of the CARS2 total score.

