A dataset is said to have a monotone missing pattern if missing values always occur at the end of data records; if we note $Y_i = (Y_{i,0}, Y_{i,1}, \dots, Y_{i,t}, \dots, Y_{i,T})$ the measured variable at each time t from baseline ($t=0$) to the end of the study ($t=T$) for an individual i , the missing pattern is monotone if, for all individuals and all times, if $Y_{i,t}$ is missing, then $Y_{i,t+1}$ is also missing and if $Y_{i,t}$ is not missing, then $Y_{i,t-1}$ is not missing also.

A total of 100 imputed partially completed datasets will be generated.

In case of patients with no data available at baseline and at any post baseline visit, a regression method will be used on the 100 imputed partially completed datasets to perform the imputation at the baseline visit only, using in this order: baseline covariates (*e.g.* country, gender), treatment in the model.

This dataset will serve as a basis for Step 2a and Step 2b (*DATA_BASIS*).

For the following step, the entry dataset will be sorted by imputation, by treatment and by patient.

Step 2:

In this sequence, remaining missing data of *DATA_BASIS* will be imputed. The treatment group and the reason for study or drug premature withdrawals have to be considered as the imputation rules will be different. For this imputation step, countries with less than 10 patients will be gathered to avoid strata with no observed values.

a) For all placebo patients and patients in S95008 arm with study or drug premature withdrawals due to other reasons:

To impute those missing data, all data will be considered (regardless of the treatment and of the reason of withdrawal) in order to benefit of all data available at each visit. However, at the end, only data (imputed or initially complete) from all placebo patients and data from S95008 patients, completers or with initially missing data due to other reasons will be considered (the other being imputed with jump-to-placebo method, as explained in step 2b).

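### The treatment-policy analysis of CARS2 imputes some bumetanide children who stopped as if still on drug, and no planned analysis varies that (minor)

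*SAP*

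**What the plan says.** The treatment-policy item in SAP 3.4.2.3 repeats the primary analysis "using all CARS2 values reported regardless of occurrence of treatment discontinuation". It then adds: "In case of CARS2 values are still missing, the same imputation process as in the primary analysis will be performed for these individuals".

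The primary process (SAP 3.4.2.1) has two branches for the S95008 arm.

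- **Stopped for adverse event or lack of efficacy:** jump-to-reference, on the ground that "the assumption that the treatment benefit in patients who discontinue the active arm disappears immediately upon discontinuation is clinically meaningful".
- **Stopped for any other reason:** "missing data will be imputed in both arms using a multiple imputation based on similar patients in the same treatment arm". The target is the difference had no such stops occurred, "namely if patients were stayed under their randomised treatment".

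Appendix 5.1.2 implements the second branch (Step 2a) as one regression in which "all data will be considered (regardless of the treatment and of the reason of withdrawal". Treatment is a term in that regression, and there is no indicator for being off drug. Step 1 of the same appendix sets data collected after treatment withdrawal to missing and does not exempt the treatment-policy run.

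Protocol 4.2.2 and 5.6.1 ask children who stop drug to return for CARS2 at W026. They do not return if fewer than two months remain, or if background care has changed in an important way.

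**The concern.** A treatment-policy estimand asks what happens to children as randomised, including those who are off drug. A child who stopped for an other reason and has no rating near week 26 is given a score that answers a different question, namely what would have happened on continued treatment. If benefit fades after stopping, the estimate leans towards bumetanide.

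Readers will use this analysis to check the hypothetical primary estimand. For the unobserved children, agreement between the two is partly built in. Protocol 10.2.2.4.2 promises sensitivity analyses to the missing-data method. The one analysis listed under that title in SAP 3.4.2.2 only drops country and gender.

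**Working it through.** **1. What each planned CARS2 analysis does with a bumetanide child who stopped for an other reason and has no W026 rating**

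| Analysis | Handling |
|---|---|
| Primary (3.4.2.1) | Missing at random, by arm |
| Unadjusted (3.4.2.2) | Same process; country and gender dropped |
| Treatment policy (3.4.2.3) | Same process; the regression also sees observed off-drug values |
| MMRM (3.4.2.3) | "In this analysis, all data occurring after all intercurrent events will be considered as missing"; run "will be performed as if patients had continued their randomised treatment" |
| W012 analysis | Primary method repeated |
| Responders | Derived from the same imputed datasets |

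None departs from missing at random for this child.

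**2. Who these children are.** They are those lost to follow-up, those whose consent was withdrawn, those with an important change of care, and some late stoppers. For stops at W020 or W026, Table (4.2.2) 2 marks the W026 visit as not applicable but schedules the withdrawal visit (WD) and the follow-up visit (Wend). The investigation schedule places CARS2 at both. Wend is six weeks after stopping, so a W020 stop gives a Wend rating at week 20 + 6 = 26. The SAP has no rule that places it at W026.

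**3. Inputs**

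- d = 0.15 stop (Protocol 10.1, SAP 1.3). The plan's own figures reproduce: 2(1.96 + 1.28)²/0.5² gives 85 per arm, 170 in total, and 170/(1 − 0.15) = 200. The 15% is not split by reason or arm.
- D = 3 points, an assumption close to the 3.06 points reported for phase IIb in Protocol section 2. SD = 3/0.5 = 6.
- s = share of stops for other reasons: assumed 1/3 to 2/3.
- m = share of stoppers with no rating. With uniform timing, the two-month rule gives 8.67/26 = 0.333.
- r = share of benefit that other-reason stoppers retain. Adverse-event and lack-of-efficacy stoppers are taken to retain none.

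**4. Formulas**

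- Truth = D[(1 − d) + d·s·r]
- Planned = D[(1 − d) + d·s·(m + (1 − m)r)], so the error is +D·d·s·m·(1 − r)
- Jump-to-reference for the same children: error −D·d·s·m·r

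**5. Results at r = 0** (truth = 3 × 0.85 = 2.55 points)

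| Who is unrated | m | Children per 100 | Error, points | Overstatement |
|---|---|---|---|---|
| Two-month rule only | 0.333 | 1.7–3.3 | 0.05–0.10 | 2.0–3.9% |
| Same, but Wend ratings within 2 weeks of W026 used | (8.67 − 4)/26 = 0.18 | 0.9–1.8 | 0.03–0.05 | 1.1–2.1% |
| Every other-reason stopper | 1 | 5–10 | 0.15–0.30 | 5.9–11.8% |

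In the second row, stops from W018 to W022 have Wend between W024 and W028. That recovers 4 of the 8.67 weeks.

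At r = 0.5 the errors in points halve. For the first row they are 0.025–0.05 against a truth of 2.625–2.70, or 1.0–1.9%.

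The standard error with 100 per arm is 6√(2/100) = 0.85 points. The errors at r = 0 without Wend ratings (first and third rows) are therefore 0.06 to 0.35 standard errors.

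**6. How jump-to-reference compares.** In the closed form the two errors are equal and opposite at r = 0.5, and jump-to-reference is the closer below that. A large simulation (visits correlated 0.65, two-month rule only, s = 1/3 to 2/3, r = 0) gave +2.0 to +3.6% for the planned method and +0.2 to +0.4% for jump-to-reference. Both lie above the truth, so the two runs need not bracket it.

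**The case against.** The case for leaving the plan alone is substantial, and most of it stands.

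- **Observed values are used.** Stoppers rated at W026 contribute their real scores, those scores enter the Step 2a regression, and a child's own earlier ratings are conditioned on. A reader might infer that this analysis is the primary one under another name. It is not. The mismatch is confined to children with no usable rating.
- **Late stoppers are not without data.** A reader might take the missing W026 visit after a W020 stop to mean that nothing was collected. WD and Wend ratings are scheduled. For these children the gap is mainly a missing visit-mapping rule.
- **The primary handling matches its own estimand.** Missing at random fits the hypothetical strategy stated for other-reason stops. Jump-to-reference for all stops in the primary model would answer another question.
- **The loss-of-benefit premise is stated only for adverse-event and lack-of-efficacy stops.** If more than half the benefit persists off drug, jump-to-reference is further from the truth than the plan.
- **The protocol names the MMRM, and the SAP includes it.** This meets the promise only in part, because the MMRM keeps the same assumption for these children.
- **Tabulations may exist elsewhere.** SAP 3.2.1 plans withdrawal reasons, a Kaplan-Meier analysis by reason and a listing of treatment-withdrawn completers. Table templates are in a separate document, so a missing count cannot be asserted.

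A reader might also infer a threat to power. If 5–15% of the bumetanide arm moved to jump-to-reference in the tested analysis, power at 85 per arm would fall from 90.3% to 87.2–79.1%. That describes a change to the primary analysis, which is not proposed here.

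**Conclusion.** The point holds as a minor improvement. For bumetanide children who stopped for other reasons and have no off-drug rating near week 26, the imputation in the treatment-policy run does not match its label, and nothing planned tests it.

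If benefit is lost on stopping, the overstatement is about 2–4% under the two-month rule alone, about 1–2% once nearby Wend ratings are used, and about 6–12% if every other-reason stopper is unrated. The figures roughly halve if half the benefit is retained. A bound near 18% (0.15/0.85) needs every stop to be for an other reason and no stopper to be rated. Nothing in the documents points to that.

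The other-reason share, the timing, the retention and the 3-point effect are all assumptions. The documents do not support any claim about the primary test, sample size or type I error. The estimate concerned is supplementary and, under SAP 3.4.1, carries no p-value.

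**What to change.** 1. In the treatment-policy run, use an off-drug Wend CARS2 that falls near week 26 as the W026 value, with the window stated. Say that the Step 1 rule setting post-withdrawal data to missing does not apply to this run.
2. Impute the remaining off-drug S95008 children without a W026 value by jump-to-reference, whatever the reason for stopping. Show the planned missing-at-random version beside it.
3. Report observed and imputed W026 values after discontinuation by arm and reason.

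Optionally, add the primary model with jump-to-reference for all S95008 stops, labelled supplementary because it targets a different estimand.

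The cost is SAP wording, one table and one or two re-runs with the %mistep macro already planned in Appendix 5.1.2. The supplementary estimate may come out slightly less favourable. Jump-to-reference is itself an assumption: it understates the effect to the extent that benefit persists off drug, and does not represent new care started after stopping.
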